1.0 Objectives

1.1 Study Objectives

The long-term objective of this study is to determine whether a glucagon-like peptide-1 receptor (GLP-1R) agonist, liraglutide (brand name is Saxenda®), can improve clinical outcomes in patients with opioid use disorder (OUD). We propose to study the efficacy and safety of liraglutide treatment and its effects on craving in OUD patients within a randomized, placebo controlled, double-blinded, parallel arm clinical pilot study with two objectives:

- 1) To evaluate the efficacy of liraglutide (vs placebo), administered daily, in reducing craving for opioids in humans in residential treatment for an OUD. Well-validated measures of craving, including visual cue-elicited craving, and ecological momentary assessment (daily smartphone assessments) will be used to assess craving. Based on our preclinical studies, we hypothesize that liraglutide will decrease craving among patients in treatment for OUD.
- 2) To evaluate the safety of liraglutide, administered daily, in humans seeking treatment for OUD. We will measure how liraglutide changes respiratory rate, blood pressure, and heart rate as well as blood concentrations of glucose, hemoglobin A1c (HbA1c), and fructosamine, over the course of a 18-day titration (3-dose intervention) or 30-day titration (5-dose intervention) to full treatment dosage.

1.2 Primary Study Endpoints

The primary objectives of this pilot study are 1) to determine whether liraglutide can reduce cue-elicited drug craving over 3-5 weeks while participants are in residential treatment for OUD, and 2) to study whether liraglutide can reduce ambient (daily) drug craving over approximately 21-33 days while participants are in residential treatment for OUD.

- 1) Cue-elicited Drug Craving. Change in self-reported cue-elicited drug craving from baseline (Day 1) to the end of the target drug dose (Day 19 [and additionally until Day 31 for 5-dose intervention]) will be measured on a 0-100 point visual analog scale (VAS), where 0= no craving, 100= maximum craving. Assessments are taken prior to, and immediately after, exposure to visual drug cues in the Cue Response Task.
- 2) Ambient Drug Craving. Change in ambient drug craving over time will be measured throughout the study (Days 1-21 [and additionally until Day 33 for 5-dose intervention]) using a 0-100 VAS delivered via smartphone using Ecological Momentary Assessment (EMA) 4 times per day, on each test day (Days 1 and 19 [and additionally Day 31 for the 5-dose intervention]) and on the first two days and last 2 days of each treatment dose.

1.3 Secondary Study Endpoints

The secondary objective of this pilot study is to evaluate the safety of daily administration of liraglutide in humans seeking treatment for an OUD.

1) Cardiorespiratory Function

- a. *Blood Pressure*. Change in blood pressure from baseline (Day 1) to: i) the beginning of each study drug dose (Days 2, 8, 14, 20, 26); ii) end of the target drug dose (Day 19 [Day 31 for 5-dose intervention]); and iii) rebound follow-up (Day 21 [Day 33 for 5-dose intervention]).
- b. Heart Rate. Change in heart rate from baseline (Day 1) to: i) the beginning of each study drug dose (Days 2, 8, 14, 20, 26); ii) end of the target drug dose (Day 19, [Day 31 for 5-dose intervention]); and iii) rebound follow-up (Day 21 [Day 33 for 5-dose intervention]).
- c. *Respiration*. Change in respiratory from baseline (Day 1) to: i) the beginning of each study drug dose (Days 2, 8, 14, 20, 26); ii) end of the target drug dose (Day 19 [Day 31 for 5-dose intervention]); and iii) rebound follow-up (Day 21 [Day 33 for 5-dose intervention]).

- 2) **Body Weight** (*kg*). Absolute and percent change in body weight from baseline through the end of rebound follow-up (Daily, from Days 1 to 21 [Days 1-33 for 5-dose intervention]).
- 3) **Glycemic Control.** Glycemic control will be monitored by fasting blood samples for fructosamine and A1c. Fasting blood sample measurements change slowly overtime (i.e., across weeks and months) and therefore will be evaluated only on Days 2 and 19 [and additionally Day 31 for 5-dose intervention] via venipuncture.
- 4) Adverse Events. Frequency of adverse events (AE) and serious adverse events (SAE) deemed related to treatment throughout the study period (Days 1-21 [1-33 for 5-dose intervention]), and at 30 days post-intervention (Day 49 [Day 61 for 5-dose intervention]).

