1.4 Exploratory Endpoints

- 1) **Prefrontal Cortical Response to Drug Cues.** Change in blood oxygenation level response to visual opioid drug cues in prefrontal cortex from baseline (Day 1) to end of the target drug dose (Day 19 [additionally Day 31 for 5-dose intervention]) using Functional Near Infrared Spectroscopy (fNIRs).
- 2) **Rebound Ambient Drug Craving.** Change in ambient drug craving as measured by 0-100 VAS delivered via smartphone using the EMA on test days and on the first two days and last 2 days of each treatment dose from end of rebound follow up (Day 21 [Day 33 for 5-dose intervention]) to baseline (Day 1) and to end of the target drug dose (Day 19 [Day 31 for 5-dose intervention]).
- 3) **Rebound Blood Pressure.** Change in blood pressure from end of the target drug dose (Day 19 [Day 31 for 5-dose intervention]) to rebound follow up (Day 21 [Day 33 for 5-dose intervention]).
- 4) **Rebound Heart Rate.** Change in heart rate from end of the target drug dose (Day 19 [Day 31 for 5-dose intervention]) to rebound follow up (Day 21 [Day 33 for 5-dose intervention]).
- 5) **Rebound Respiration.** Change in respiratory from end of the target drug dose (Day 19 [Day 31 for 5-dose intervention]) to rebound follow up (Day 21 [Day 33 for 5-dose intervention]).
- 6) **Long-term Glycemic Control.** Change in HbA1c and fructosamine levels from Day 2 to end of the target drug dose (Day 19 [Day 31 for 5-dose intervention]).

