7.2.5 Study Test Day – (Day 19)

The following **research-only** measures, all completed on Day 1, will be repeated on Day 19, regardless of intervention length (i.e., 3-dose and 5-dose interventions). Day 19 will serve as the final dose (1.8 mg) day for participants in the 3-dose intervention. For participants in the 5-dose intervention, Day 19 will be the final day at the 1.8 mg dose before moving on to the 2.4 mg dose on Day 20.

- Cardiorespiratory function will be assessed via measurement of blood pressure, heart rate, and respiratory rate as described in Section 7.2.
- Blood samples will be collected for safety laboratory tests (CBC, CMP) and for monitoring of glycemic control. Approximately 4 teaspoons of blood will be collected.
- Body weight data will be collected.

- Cue-elicited drug craving will be evaluated using VAS.
- Neurophysiology measurements will be evaluated using fNIRS during: (1) Visual cue reactivity and (2) BART.
- Collection of ambient drug craving, mood, and sleep data by EMA.
- Stress response, sleep, and activity measurements will be collected via actigraphy wristband.
- C-SSRS
- Urine pregnancy test (if applicable)
- Aes and concomitant medications will be documented.

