7.2.8 Study Drug Treatment, Dose 5 (Days 26-30) [5-dose intervention only]

During this time, the following research-only activities will occur:

- During Days 26-31, 3.0 mg of liraglutide/placebo control will be administered daily at a specified time (prior to breakfast).
- o Aes and concomitant medications will be documented.

- Ambient drug craving, mood, and sleep data will be collected on Days 26, 27, and 30 via EMA assessment.
- Stress response, sleep, and activity measurements will be collected daily via actigraphy wristband.
- Body weight data will be collected daily.
- On Day 26, cardiorespiratory function will be measured as described in Section 7.2.

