For exploratory outcomes, analysis of fNIRs-based neuroimaging will utilize a 2 (Medication Status) x 2 (Medication Type) ANOVA to evaluate the change in oxygenation in prefrontal cortex in response to opioid drug cues vs neutral cues, with a region of interest in left middle frontal gyrus. Analysis of safety outcomes from baseline to the end of target dose and to end of rebound follow-up will be analyzed using intensive longitudinal methods similar to the analysis of secondary outcomes. Changes in indices of glycemic control measured at baseline and at end of the target dose (e.g. HgA1c, fructosamine) will be calculated as deltas, with comparisons made between treatments using unpaired t-tests or Mann Whitney U tests as appropriate.

Interim Power Analysis: one or more interim power analyses may be conducted during the study to assess the effect size needed to observe a significant drug effect for primary, secondary, and/or exploratory endpoints based on the data collected at that time. These analyses would not bias type 1 error rates and the study team will use this information to determine whether and when to perform an interim data analysis to justify advancement to the second phase of the funding award (UH phase). In particular, the confidence intervals around the parameters representing the primary endpoint will be used as an approximation of the power available for our primary endpoints using the current data. This

will be weighed against the original proposed power and the PI's estimates of likely power after completion of the grant period to determine whether an interim analysis is warranted.

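### The end-of-dose value for cardiorespiratory and exploratory endpoints 2 to 6 moves from Day 19 (1.8 mg) to Day 31 (3.0 mg) with a course length chosen after randomisation, so the arm contrast has no single dose or day

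*Combined protocol and SAP*

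**What the plan says.** Section 1.3 defines the change in blood pressure, heart rate and respiration to "end of the target drug dose (Day 19 [Day 31 for 5-dose intervention", and then to "rebound follow-up (Day 21 [Day 33 for 5-dose intervention". Section 1.4 repeats the construction for exploratory endpoints 2 to 6: rebound craving, rebound blood pressure, heart rate and respiration, and for the last, "Change in HbA1c and fructosamine levels from Day 2 to end of the target drug dose (Day 19 [Day 31 for 5-dose intervention". In each, Day 31 stands in place of Day 19 for the 5-dose course.

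Elsewhere Day 31 is an addition. The primary cue-craving endpoint in section 1.2 runs to "end of the target drug dose (Day 19 [and additionally until Day 31 for 5-dose intervention". Secondary glycaemic control in section 1.3 is "evaluated only on Days 2 and 19 [and additionally Day 31 for 5-dose intervention] via venipuncture". The fNIRS endpoint in section 1.4 is worded the same way.

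The two days carry different doses. Section 7.2.5 states "Day 19 will serve as the final dose (1.8 mg) day for participants in the 3-dose intervention", and section 7.2.8 states "During Days 26-31, 3.0 mg of liraglutide/placebo control will be administered daily".

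Under section 7.1 everyone starts on the 3-dose course. By Day 18 each participant is asked about extending, and the answer depends on length of stay and on the participant's own choice. No expected share of extenders is given.

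Section 8.3 plans time-varying effect models for the repeatedly measured safety outcomes. For exploratory glycaemia it takes "Changes in indices of glycemic control measured at baseline and at end of the target dose", forms a delta, and compares arms by unpaired t-test or Mann-Whitney. Neither analysis has a term, stratum or separate estimate for course or current dose.

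**The concern.** One endpoint label covers two doses and two durations, and what decides between them is settled after randomisation, when up to 17 days of blinded drug have been taken (Days 2 to 18). An arm difference built on that label answers neither the 1.8 mg question nor the 3.0 mg question; its value depends on how many people happened to stay on. Extension could also depend on treatment, through tolerability or craving, and participants withdrawn earlier cannot extend.

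This matters because section 2.3 makes demonstrated safety part of the case for the next, multi-centre trial. A heart-rate or blood-pressure contrast that cannot be tied to a dose is weak support for that decision.

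**Working it through.** **The plan's own figure.** Section 8.2 gives 80% power for an effect of 0.91 with 20 per group, two-sided 0.05. The exact t-test has 38 degrees of freedom and noncentrality 0.91 × √(20 × 20/40) = 2.88, giving 80.1%. Attrition: 40/0.8 = 50. Both reproduce. They concern cue-elicited craving; the documents give no power figure for the safety endpoints.

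**What each label contains, from the schedule.**

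| Endpoint | 3-dose course | 5-dose course |
|---|---|---|
| Cardiorespiratory, Day 1 to end of dose | 19 − 1 = 18 days, 1.8 mg | 31 − 1 = 30 days, 3.0 mg |
| Exploratory HbA1c and fructosamine, Day 2 to end of dose | 19 − 2 = 17 days, 1.8 mg | 31 − 2 = 29 days, 3.0 mg |
| Rebound, two days after last dose | Day 21, after 1.8 mg | Day 33, after 3.0 mg |

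**What the longitudinal models would see.** On Days 20 and 21, 3-dose participants are off drug while 5-dose participants receive 2.4 mg (section 7.2.6). By the schedule footnotes, cardiorespiratory data on Day 20 come only from the 5-dose course and on Day 21 only from the 3-dose course. Days 26, 31 and 33 are again 5-dose only. After Day 19, study day alone therefore identifies neither dose nor a randomised population.

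**Meaning of a single pooled value.** Let f be the share extending, d19 the drug effect at Day 19 and d31 the effect at Day 31. With equal f in both arms:

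pooled effect = (1 − f) × d19 + f × d31

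Assume d19 = 0.50 SD and d31 = 0.91 SD:

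- f = 20%: 0.8 × 0.50 + 0.2 × 0.91 = 0.58 SD
- f = 30%: 0.7 × 0.50 + 0.3 × 0.91 = 0.62 SD
- f = 50%: 0.5 × 0.50 + 0.5 × 0.91 = 0.71 SD

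**Bias when the drug does nothing.** Let m be the average change from Day 19 to Day 31 among extenders that is not due to drug. Then

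bias = f(liraglutide) × m(liraglutide) − f(placebo) × m(placebo)

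This is zero when both quantities are equal by arm. With a common m it is the difference in extension rates times m. Type I error below is from 40,000 simulated t-tests with 20 per arm:

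| Extension, liraglutide vs placebo (assumed) | m (assumed) | Bias | Type I error |
|---|---|---|---|
| 30% vs 30% | 0.5 or 1 SD | 0 | 5% |
| 20% vs 40% | 0.5 SD | −0.20 × 0.5 = −0.1 SD | 6.2% |
| 20% vs 40% | 1 SD | −0.20 × 1 = −0.2 SD | 8.6% |
| 20% vs 60% | 0.5 SD | −0.40 × 0.5 = −0.2 SD | 9.2% |
| 20% vs 60% | 1 SD | −0.40 × 1 = −0.4 SD | 20.3% |

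This calculation describes a one-value-per-person comparison. That is the stated analysis for the glycaemic delta, but not for the cardiorespiratory measures.

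**After separating the days.** Day 19 keeps all 20 evaluable per arm at one dose: 80.1% power for 0.91 SD. Day 31 alone, if 20%, 30% or 50% extend (assumed), has 4, 6 or 10 per arm. Its detectable effect at 80% power is 2.38, 1.80 or 1.32 SD, and its power for 0.91 SD is 19%, 30% or 49%.

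**The case against.** The documents nowhere state that Day 19 and Day 31 values enter one contrast. Blood pressure, heart rate and respiratory rate go into time-varying effect models, which represent time explicitly and need not reduce to a last value. That stands: for these measures the gap is an endpoint that swaps days plus a model with no stated course or dose term, not a declared pooled t-test. It does not rescue the exploratory glycaemic delta.

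Both arms are blinded and both may extend, and some participants know their length of stay at admission. That also stands. A reader might infer that the safety contrasts are biased, but no figure in the documents suggests that extension differs by arm, and with equal extension the type I error stays at 5%.

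A reader might also put the bias in natural units, as 12 days times a daily drift times the difference in extension rates. The documents give no drift. A drift of 0.5 to 1.0 unit per day means 6 to 12 units between Days 19 and 31, which for respiration exceeds the change of 5 breaths per minute that section 3.3.1 uses as a withdrawal limit. For HbA1c it conflicts with section 1.3, which describes these markers as slow to change. I give no such range.

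Nor does the point reach every safety endpoint. Secondary glycaemic control already keeps Day 19, and body weight is a daily endpoint not defined by this bracket.

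Finally, section 8.2 calls this an exploratory pilot, and these are not powered endpoints. That limits the weight of the point, but not the case for a nearly free clarification.

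**Conclusion.** The point holds in a limited form. Taken as written, the end-of-dose definition for the three cardiorespiratory endpoints and exploratory endpoints 2 to 6 depends on a non-randomised course length, and section 8.3 does not resolve it. The exploratory HbA1c and fructosamine comparison mixes 17-day and 29-day changes at two doses; the cardiorespiratory models leave the matter open.

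The certain cost is interpretability: the contrast belongs to no single dose or day. Bias between arms is conditional on the extension rate, or the kind of patient extending, differing by arm. Under assumed rates of 20% and 40% and a shift of 0.5 to 1 SD it is about 0.1 to 0.2 SD for a single-value comparison. Extension rates, shifts and drug effects are all my assumptions. The primary craving endpoint's wording is not touched by this point.

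**What to change.** - In sections 1.3, 1.4 and 8.3, use the form already found in section 1.2: Day 19, and *additionally* Day 31 for the 5-dose course. This keeps both time points and does not relabel the target dose.
- Make the change to Day 19 in all participants the randomised between-arm contrast.
- Report the Day 31 change, and the Day 21 and Day 33 rebound values, separately by course, with the extension rate by arm.
- In section 8.3, either include current dose or course in the longitudinal safety models, or limit the between-arm comparison to data through Day 19.
- Reconcile section 9.4, whose 5-dose cardiorespiratory day list omits Day 19, with sections 7.2 and 7.2.5 and the 5-dose schedule, which include it. The common contrast depends on that visit.

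The cost is wording and model specification. Section 7.2.5 already schedules Day 19 testing whatever the course, so no visit is added once section 9.4 is reconciled. The downside is that the 3.0 mg result becomes a separate, small and descriptive estimate.

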Data reduction including derivation of summary features for continuously collected data (e.g., sleep data, physiological data) will be performed before formal statistical analysis. Descriptive analysis will be performed to explore distributions of data and identify potential outliers. Assumptions and goodness of fit of statistical models will be assessed. Missing data, including mobile and ambulatory attrition and drop-out will be examined to ensure the validity of statistical models used. Because ambulatory and mobile monitoring will continue during laboratory assessment days, correlation analyses will be used to confirm the agreement between corresponding measures from the two approaches; this will both speed harmonization for follow-up analyses, and provide additional validation of the measures used in the both cases.

The primary endpoints of the EMA assessment will be the rate of reduction of craving across the approximately 21 day study period in the treatment condition compared to the control condition while controlling for the traditional craving triggers of sleep, stress, hunger, affect, and pain and discomfort. Sleep and activity will be measured using a multimodal approach with self-report via the morning EMA survey and wearable actigraphy to measure and account for subjective biases in sleep timing. Craving reduction will be primarily measured using EMA assessment, and will be modeled using linear mixed models in the multilevel modeling (MLM) framework. In MLM, subject-specific random effects are combined with population-level fixed effects to account for variability both within each individual and between individuals in a manner that allows participants with incomplete data to be included in the model. Craving reduction will be modeled as an effect of time in treatment, and differences in rate of craving reduction will be tested as an interaction between treatment state and time. Drs. [name], [name], and [name] each have extensive experience analyzing similar data in the multilevel modeling framework.

For secondary safety outcomes, intensive longitudinal methods such as time-varying effect models will be used to assess for changes in continuously measured outcomes (e.g. blood pressure, heart rate, respiratory rate, body weight) to account for repeated measures. The proportion of participants experiencing AE and SAE will be compared between treatments using chi-square analysis.

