9.0 Data and Safety Monitoring Plan

9.1 Periodic evaluation of data

To monitor safety throughout the course of the study, every effort will be made to remain alert to possible Aes/SAEs. If an AE/SAE occurs, the first concern should be for the safety of the subject; CaronTC's medical staff is available 24/7 and will be immediately alerted in the event of a SAE. If necessary, appropriate medical intervention will be provided. At the signing of the written consent form, each subject will have been given the names and telephone numbers of study site staff for reporting Aes/SAEs and medical emergencies.

In this study, any AE/SAE experienced by the subject between the time of first dose of study treatment and 24 hours after the last dose will be recorded on the case report form, regardless of the severity of the event or its relationship to study treatment. During study treatment, the research team will assess the subject for Aes and will record any new Aes/SAEs or updates to previously reported Aes on the electronic case report form.

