9.2 Data that are reviewed

Data collected as primary outcomes, secondary outcomes, exploratory outcomes, and safety profile for the study will be reviewed. Primary outcomes include cue-elicited drug craving and ambient drug craving. Secondary outcomes include blood pressure, heart rate, respiration, body weight, and AE. Exploratory outcomes include prefrontal cortical response to drug cues, markers of long-term glycemic control and rebound in ambient drug craving, blood pressure, heart rate, and respiration.

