18.0 Adverse Event Reporting

18.1 Adverse Event Definitions

Adverse event	Any untoward medical occurrence associated with the use of the drug in
	humans, whether or not considered drug related
Adverse reaction	An Adverse Reaction is an adverse event for which the causal relationship
	between the drug and the adverse event is suspected.
Suspected adverse	Any adverse event for which there is a reasonable possibility that the drug
reaction	caused the adverse event. Suspected adverse reaction implies a lesser degree
	of certainty about causality than "adverse reaction".
	 Reasonable possibility. For the purpose of IND safety reporting,
	"reasonable possibility" means there is evidence to suggest a causal
	relationship between the drug and the adverse event.
Serious adverse	Serious adverse event or Serious suspected adverse reaction: An adverse event
event or Serious	or suspected adverse reaction that, in the view of either the investigator or
suspected adverse	sponsor, results in any of the following outcomes: Death, a life-threatening
reaction	adverse event, inpatient hospitalization or prolongation of existing
	hospitalization, a persistent or significant incapacity or substantial disruption
	of the ability to conduct normal life functions, or a congenital anomaly/birth
	defect. Important medical events that may not result in death, be life-
	threatening, or require hospitalization may be considered serious when, based
	upon appropriate medical judgment, they may jeopardize the patient or
	subject and may require medical or surgical intervention to prevent one of the
	outcomes listed in this definition. Suspicion of transmission of infectious
	agents must always be considered a serious adverse event.
Life-threatening	An adverse event or suspected adverse reaction is considered "life-
adverse event or	threatening" if, in the view of either the Investigator (i.e., the study site
life-threatening	principal investigator) or sponsor, its occurrence places the patient or research
suspected adverse	subject at immediate risk of death. It does not include an adverse event or
reaction	suspected adverse reaction that had it occurred in a more severe form, might
I I a a a a a a a a a a a a a a a a a a	have caused death.
Unexpected	An adverse event or suspected adverse reaction is considered "unexpected" if
adverse event or	it is not listed in the investigator brochure, not listed as per the reference

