18.3 Causality and Severity Assessments

The investigator will promptly review documented adverse events and abnormal test findings to determine 1) if the abnormal test finding should be classified as an adverse event; 2) if there is a reasonable possibility that the adverse event was caused by the study drug(s) or device(s); and 3) if the adverse event meets the criteria for a serious adverse event.

If the investigator's final determination of causality is "unknown and of questionable relationship to the study drug(s) or device(s)", the adverse event will be classified as associated with the use of the study drug(s) or device(s) for reporting purposes. If the investigator's final determination of causality is "unknown but not related to the study drug(s) or device(s)", this determination and the rationale for the determination will be documented in the respective subject's case history.

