19.1.2 Safety Monitoring

The PI will confirm that all AE are correctly entered into the AE case report forms by the coordinator; be available to answer any questions that the coordinators may have concerning AEs; and will notify the IRB and/or DSMB of all applicable AEs as appropriate. All AE assessments will be made by the PI AND one of the following: Dr [name] (physician and study team member), the medical monitor, or Dr [name] (physician and study team member).

The Research Coordinator will complete the appropriate report form and logs; assist the PI to prepare reports and notify the IRB and/or DSMB of all Unanticipated Problems/SAE's.

The Monitor will confirm that the AEs are correctly entered into the case report forms. The Monitor will also confirm that the adverse events are consistent with the source documents and are reported to the appropriate regulatory bodies as required.

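### The adverse event endpoint in 1.3 can be read as counting only events judged related to treatment, while recording, definition and analysis carry no such limit; make it all-cause and align the sections

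*Combined protocol and SAP*

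**What the plan says.** All references are to the combined protocol and SAP.

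- **Endpoint, 1.3(4):** "Frequency of adverse events (AE) and serious adverse events (SAE) deemed related to treatment throughout the study period". The period is Days 1-21 (Days 1-33 for the 5-dose intervention), plus 30 days post-intervention (Day 49 or Day 61). Grammatically, the relatedness phrase may apply to AEs and SAEs or to SAEs alone.
- **Recording, 9.1:** "any AE/SAE experienced by the subject between the time of first dose of study treatment and 24 hours after the last dose will be recorded", and this is to be done "regardless of the severity of the event or its relationship to study treatment".
- **Definition, 18.1:** an AE is an untoward medical occurrence associated with use of the drug in "humans, whether or not considered drug related".
- **Outcome list, 9.2:** "Secondary outcomes include blood pressure, heart rate, respiration, body weight, and AE", without a qualifier.
- **Analysis, 8.3:** "The proportion of participants experiencing AE and SAE will be compared between treatments using chi-square analysis", again without a qualifier.
- **Who judges:** under 18.3 the investigator decides whether drug causation is a reasonable possibility. Under 19.1.2, "All AE assessments will be made by the PI AND one of the following", meaning a study physician or the medical monitor.

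No section says whether the 8.3 comparison uses all events or only related ones, or that both will be reported.

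**The concern.** Two analysts could follow this plan and produce different safety results, one on all events and one on related events. Nothing fixes the choice before the data are seen.

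In a randomised placebo-controlled trial, the comparison between arms already addresses causation. Filtering each event by judged relatedness puts an opinion between the data and that comparison. Assessors tend to attribute the events they already expect, so the filter is least reliable for effects nobody has foreseen. That matters here: section 10.0 says liraglutide has not been given before in OUD and that unknown risks may exist, and 2.3 makes demonstrated safety one condition for moving to a multi-center trial.

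Attribution could also differ by arm. Section 10.0 lists nausea, diarrhea, vomiting and decreased appetite as common effects. If these lead an assessor to suspect liraglutide, that participant's other events may be called related more readily.

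**Working it through.** **1. The plan's own figure.** Section 8.2 gives 20 per group, 80% power, effect size 0.91, two-sided t-test at 0.05, and 20*2/0.8 = 50 randomised. This reproduces: noncentral-t power is 0.801. It concerns craving. The documents give no figure for the AE endpoint, so no stated number is in error.

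**2. Sections side by side.**

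| Feature | 1.3(4) | 9.1 | 8.3 |
|---|---|---|---|
| Relatedness | Related only (AEs and SAEs, or SAEs alone) | Any relationship | Not stated |
| Measure | Frequency of events | Each event recorded | Proportion of participants |
| Window | Day 1 to the 30-day call | First dose (Day 2) to 24 hours after last dose | Not stated |

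The sections disagree or are silent on all three features. On the window, the last dose falls on Day 19 (3-dose) or Day 31 (5-dose), so 9.1 stops about Day 20 or Day 32, while the endpoint runs to Day 49 or Day 61. Section 7.2 and the schedules do document AEs on Day 1, through Day 21 or 33, and at the call, but only 9.1 carries the instruction to ignore relationship.

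**3. Illustration of arm-dependent attribution.** Inputs: 25 per arm (50 randomised 1:1, from 8.2 and 7.4.3). Assumptions, none from the documents: 60% of participants have an AE in both arms, there is one event per affected participant, and 40% of placebo-arm events are called related. The related rate is AE rate × attribution. The rejection probability sums the product of the two binomial probabilities over all tables where the uncorrected Pearson chi-square exceeds 3.841.

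| Attribution, liraglutide v placebo | Related rates | Chance of p < 0.05 |
|---|---|---|
| No filter (all AEs) | 0.60 v 0.60 | 0.060 |
| 60% v 40% | 0.36 v 0.24 | 0.159 |
| 70% v 40% | 0.42 v 0.24 | 0.286 |
| 80% v 40% | 0.48 v 0.24 | 0.451 |

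The filter can also hide a difference. With true rates of 70% v 40% and attribution of 40% v 70%, the related rates are 0.7 × 0.4 = 0.28 and 0.4 × 0.7 = 0.28, so a 30-point excess disappears.

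**4. Power, same exact method, 25 per arm.**

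- *Attribution unrelated to true cause.* True rates 70% v 40% give power 0.62. With 50% attribution in both arms the rates are 0.35 v 0.20 and power is 0.23.
- *Informative attribution.* Assume background AEs in 50% of each arm and, independently, drug-caused AEs in 35% v 5%. All-cause rates are 1 − 0.50 × 0.65 = 0.675 and 1 − 0.50 × 0.95 = 0.525, with power 0.21. If 90% of drug-caused and 20% of background events are called related, the rates are 1 − (1 − 0.10)(1 − 0.315) = 0.384 and 1 − (1 − 0.10)(1 − 0.045) = 0.141, with power 0.52.

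The net effect on power is therefore indeterminate.

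**The case against.** The strongest reply is that the practical consequence is limited. Events in the 9.1 window are captured whatever their cause, 9.6 has the DSMB review common and serious AEs, and this is a secondary endpoint in a pilot. Assessors are blinded by identical pens (7.4.5), and 19.1.2 requires two assessors. Section 18.3 classes events of questionable relationship as associated, which narrows the filter, although it says this is for reporting purposes and events judged unrelated would still drop out. With blinding intact, attribution follows the type of event more than the arm. The false-positive scenario also sits awkwardly with its own premise: it holds true AE rates equal, yet the cue to the arm would be extra gastrointestinal events on liraglutide. These points stand. They make the 16-45% range a hypothetical, not a forecast.

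A reader might infer three stronger things that the documents do not support:

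- *That 8.3 definitely analyses all events.* This rests only on the absence of a qualifier. Read with 18.1 it is the natural meaning, but it could be shorthand for the endpoint in 1.3. If 8.3 is indeed all-cause, the bias never enters the planned test and the fault is only in the definition.
- *That the filter must cost power.* That holds when attribution is unrelated to true cause, but informative attribution can raise power, as shown above.
- *That the safety comparison is biased in a known direction.* No attribution rates are given, and the filter can create, dilute or hide a difference.

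What the reply does not remove is the conflict in the text, or the sensitivity of a related-only endpoint to judgement about unexpected events.

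**Conclusion.** The point holds as an inconsistency with a plausible route to bias. Section 1.3(4) sets a relatedness limit, on AEs and SAEs or on SAEs alone, that 9.1, 18.1, 9.2 and 8.3 do not carry. Followed as written, it makes the randomised safety comparison depend on investigator attribution.

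The size and direction of any bias are unknown. The 16-45% rejection rate, against 6% on all AEs, depends on the assumed 60% AE rate in both arms, 25 per arm, one event per affected participant, and arm-dependent attribution of 60-80% v 40%, which would need partial unblinding. No power loss is claimed and the sample size is unaffected. The change should be made because safety is the trial's secondary objective and the correction is cheap.

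**What to change.** - **1.3(4):** define the endpoint as the proportion of participants with at least one AE, and separately with at least one SAE, by arm, regardless of relationship to treatment. This also settles which noun the relatedness phrase modifies.
- **8.3:** state that the chi-square comparison uses this endpoint, and add a supplementary table of investigator-judged related events by arm.
- **Measure:** use proportion of participants in both sections. If event counts are also wanted, name them as a separate summary.
- **Window:** reconcile the endpoint period in 1.3(4) (Day 1 to the 30-day call) with the recording period in 9.1 (first dose to 24 hours after the last dose), and state that relationship is disregarded throughout whichever window is kept.

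The cost is small: wording, plus recording events without regard to relationship over the endpoint window at contacts already scheduled. Deleting the relatedness phrase alone would not be enough, because the measure and window mismatches would remain.
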